#### **5.1.2. Subgroup analysis of the primary outcome**

Subgroup analyses will be performed on age groups. Age will be categorised at  $\leq 18$  or more. Comparisons between groups for reversal rate after the 14-days intervention period will be analysed.

## **5.2. Secondary Outcome Analysis**

All secondary outcomes will be analysed and two-sided 95% CIs for the treatment differences in these outcomes between the two arms will be calculated and presented. Secondary outcome analyses will be based on the ITT population unless specified.

### **5.2.1. Analysis of binary outcomes**

Binary secondary outcomes will be analyzed with the same strategy and method with that is used for the primary outcome.

### **5.2.2. Analysis of continuous outcomes**

The continuous outcome will be summarised using number of subjects (n), mean, standard deviation (SD), minimum, and maximum by intervention group, and will be analysed by a GLM model with treatment as fixed effect and with normal distribution and identity link function. Difference in mean outcome and mean differences with their two-sided 95% confidence intervals between two groups will be derived from the GLM model.

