#### **2.1.2. Secondary objectives**

To make these comparisons between the two groups from the baseline (the first day of the intervention phase) to the 14th day of the intervention phase or the 14th day of the self-maintenance phase:

- (1) Change in insulin.
- (2) Change in insulin-like growth factor-1.
- (3) Change in mean blood glucose.
- (4) Change in gut microbial compositions.
- (5) Change in body weight.
- (6) Change in waist circumference.

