### **2.2.2. Secondary outcomes**

- Change in insulin measurements from fasting blood sample. (Time Frame: from the baseline (the first day of the intervention phase) to the 14th day of the intervention phase.)
- Change in insulin-like growth factor-1 from fasting blood sample. (Time Frame: from the baseline to the 14th day of the intervention phase.)
- Change in mean blood glucose. (Time Frame: from the baseline to the 14th day of the intervention phase.)
- Change in gut microbial compositions. (Time Frame: from the baseline to the 14th day of the intervention phase.)
- Change in body weight (kg). (Time Frame: from the baseline to the 14th day of the intervention phase.)
- Change in body weight (kg). (Time Frame: from the baseline to the 14th day of the self-maintenance phase.)
- Change in waist circumference (cm). (Time Frame: from the baseline to the 14th day of the intervention phase.)

- Change in waist circumference (cm). (Time Frame: from the baseline to the 14th day of the self-maintenance phase.)

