### **3.4. Randomisation**

Randomisation is stratified by two age groups and with block size of 2 and allocation of 1:1 at each stratum. The randomisation was done by Stata software version 15. For each stratum a sequence of subjects IDs and intervention allocations was generated, which by creating a random variable and ordering on that variable. After signing the informed consent form, the subjects are assigned to the experimental or the control groups and receive the designed intervention.

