### **Covariate adjusted analysis of the primary outcome**

An analysis of the primary endpoint will be adjusted for age, sex, family history of cardiovascular disease, and fasting insulin concentrations at baseline by GLM model. The model may not converge when all covariates are introduced into the model simultaneously. If this occurs, a covariate will be removed from model one by one starting from the last covariate until the model converges.

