## 8. Study variable list

NO	Variables	
	Baseline	
1	Name	T
2	Sex	B
3	Recruited date	D
4	Birth date	D
5	Height	N
6	Weight	N
7	Waist circumstance	N
8	Age	N
9	Family history of cardiovascular disease	B
10	Fasting blood glucose (mmol/L)	N
11	OGTT 2-hours glucose (mmol/L)	N
12	Glycosylated hemoglobin	N
13	Fasting insulin (mIU/L)	N
14	Total cholesterol (mmol/L)	N
15	Triglyceride (mmol/L)	N
16	High density lipoprotein (mmol/L)	N
17	Low density lipoprotein (mmol/L)	N
18	Systolic pressure (mmHg)	N
19	Diastolic pressure (mmHg)	N
20	Insulin-like growth factor-1	N
21	Gut microbial compositions	N
	Dietary intake	
22	Record date ( during 14-days intervention period )	D
23	Energy (kcal/d)	N
24	Protein (g/d)	N
25	Fat (g/d)	N
26	Carbohydrate (g/d)	N
	Continuous glucose monitoring	
27	Record date ( during 14-days intervention period )	D
28	24-hour average blood glucose	N
	At the 14th day after the dietary intervention phase	
29	Weight	N
30	Waist circumstance	N
31	Fasting blood glucose (mmol/L)	N
32	OGTT 2-hours glucose (mmol/L)	N
33	Fasting insulin (mIU/L)	N
34	Total cholesterol (mmol/L)	N
35	Triglyceride (mmol/L)	N

NO	Variables	
36	High density lipoprotein (mmol/L)	N
37	Low density lipoprotein (mmol/L)	N
38	Systolic pressure (mmHg)	N
39	Diastolic pressure (mmHg)	N
40	Insulin-like growth factor-1	N
41	Gut microbial compositions	N
	At the 14th day after the self-maintenance phase	
42	Weight	N
43	Waist circumstance	N
44	Self-reported dietary adherence	B
45	Psychological and symptoms during dietary intervention	B

Note: T, text variable; D, The date type; N, Continuous variable; B, binary variable.

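### The continuous secondary outcomes are changes from baseline but are modelled on treatment alone; adding the baseline value and the randomisation age group is a cheap gain in precision at moderate correlation

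*SAP*

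**What the plan says.** - **Model.** SAP 5.2.2 states that a continuous outcome "will be analysed by a GLM model with treatment as fixed effect and with normal distribution and identity link function". Treatment is the only term.
- **Form of the outcomes.** The lead-in to SAP 2.1.2 is "To make these comparisons between the two groups from the baseline (the first day of the intervention phase", followed by a list of changes. SAP 2.2.2 repeats this form, for example "Change in insulin measurements from fasting blood sample" and "Change in insulin-like growth factor-1 from fasting blood sample". Insulin and IGF-1 are assessed once (day 14 of the intervention phase). Weight and waist are assessed twice (also at day 14 of the self-maintenance phase). That makes six comparisons.
- **Baseline data.** The variable list in SAP section 8 has baseline weight, waist, fasting insulin and IGF-1 (items 6, 7, 13 and 20).
- **Randomisation.** SAP 3.4: "Randomisation is stratified by two age groups and with block size of 2 and allocation of 1:1 at each stratum". The age cut is not stated there.
- **Adjustment elsewhere.** The SAP plans covariate adjustment for the primary outcome only: "An analysis of the primary endpoint will be adjusted for age, sex, family history of cardiovascular disease", plus baseline fasting insulin. Nothing extends this to the secondary outcomes.

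**The concern.** A change score compared between arms with no other term leaves in the error any variation that the baseline value could explain. At moderate correlation between baseline and follow-up, the interval for the treatment difference is then wider than the data require. Leaving out a stratification factor has a related effect. Stratified allocation balances age group between the arms, but an unadjusted standard error takes no credit for that, so the interval is conservative if age group is related to the change.

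Neither omission biases the estimate or raises the false-positive rate. What is at stake is the precision of the secondary results of a pilot. The plan already uses a covariate-adjusted GLM for the primary endpoint, with baseline insulin among the covariates, yet baseline insulin is absent from the model for change in insulin.

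Mean glucose is outside this point because section 8 lists no separate baseline value for it. Gut microbial composition is also left aside.

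**Working it through.** The plan states no sample size, SD, correlation or power for these outcomes, so there is no figure to reproduce. Everything below rests on assumed values, shown as ranges.

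**Inputs.** From the SAP: 1:1 allocation, two age strata, blocks of 2, two-sided 95% intervals. Assumed: n = 10 to 30 per arm (N = 2n); correlation r of 0.5 to 0.98 between baseline and follow-up, read within age group; equal SD s at both visits unless stated.

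**Effect of the baseline term.** Var(change) = 2s²(1 − r). Residual variance given baseline = s²(1 − r²). The ratio is (1 + r)/2, that is 0.75, 0.85, 0.95 and 0.99 at r = 0.5, 0.7, 0.9 and 0.98.

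**Cost of two added terms.** The expected CI-width ratio, both terms against treatment only, when age group explains nothing, is

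[t(.975, N−4) / t(.975, N−2)] × √[(1 + r)/2 × (1 + 1/(N−5))] × c(N−4)/c(N−2), where c(v) = E√(χ²ᵥ/v).

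For n = 20 and r = 0.5: (2.0281/2.0244) × √(0.75 × 1.0286) × (0.9931/0.9934) = 1.0018 × 0.8783 × 0.9996 = 0.880.

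| n per arm | r = 0.5 | 0.7 | 0.9 | 0.98 | Break-even r | Neither term explains anything |
|---|---|---|---|---|---|---|
| 10 | 0.901 | 0.959 | 1.014 | 1.035 | 0.848 | 1.040 |
| 15 | 0.886 | 0.943 | 0.997 | 1.018 | 0.912 | 1.023 |
| 20 | 0.880 | 0.936 | 0.990 | 1.011 | 0.939 | 1.016 |
| 30 | 0.874 | 0.931 | 0.984 | 1.005 | 0.962 | 1.010 |

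The last column replaces (1 + r)/2 by 1. It is the worst average cost, whatever r or the SDs are. Simulation (20,000 runs per cell, two near-equal strata, blocks of 2) gives 0.879, 0.936, 0.990 and 1.010 at 20 per arm, and 0.901, 0.957, 1.013 and 1.034 at 10.

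**Unequal SDs.** With k = follow-up SD / baseline SD, (1 + r)/2 becomes k²(1 − r²)/(1 + k² − 2rk). At 20 per arm, for the same four values of r:
- k = 0.9: 0.830, 0.880, 0.914, 0.848
- k = 1.1: 0.918, 0.975, 1.015, 0.957

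**Effect of the age group.** If age group explains 10% of the variance of the change, simulation gives width ratios of 0.832, 0.886, 0.936 and 0.956 at 20 per arm, and 0.849, 0.903, 0.956 and 0.976 at 10.

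If the stratum is omitted, the standard error is inflated by 1/√(1 − R²) and coverage is 2Φ(1.96 × inflation) − 1:

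| R² of age group | Inflation | Coverage of nominal 95% CI |
|---|---|---|
| 5% | 1.026 | 95.6% |
| 10% | 1.054 | 96.1% |
| 20% | 1.118 | 97.2% |

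In simulation the two-term model kept coverage at 94.7% to 95.3%.

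**The case against.** The plan is valid as written. It sets no power target or decision rule for these outcomes, and no benefit can be shown from the documents: over the assumed values the width ratio runs from 0.83 to 1.035, so even its direction is open. This stands, and it keeps the point at the level of an optional improvement.

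Four of the six comparisons are weight and waist over 14 to 28 days, where the correlation may be very high. This also stands. With near-equal SDs the baseline term may then gain nothing or cost a little. It does not hold in general, because at r = 0.98 and 20 per arm a follow-up SD of 0.9 or 1.1 times baseline gives 0.848 or 0.957.

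The cost figures are averages. In simulation at r = 0.7 with no age effect, the adjusted interval was the wider one in about 40% of trials at 10 per arm and about 17% at 20. At r = 0.9 the shares were about 62% and 48%. That is true of single trials, but the expected excess stays within the worst-case column.

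A pooled correlation would misread the table. If the age groups lie 2 within-group SDs apart at both visits, a within-group r of 0.7 appears as (0.7 + 1)/(1 + 1) = 0.85. Reading the table at the pooled value understates the gain, so it does not weaken the case for the change.

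Finally, the age term cannot be written until the cut-point is known. The sponsor has that information.

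**Conclusion.** The point holds as a low-cost improvement to consider. Section 5.2.2 omits both the baseline value and the stratification factor for six change-from-baseline comparisons, and no other section supplies them. With equal SDs and no age effect, adding both narrows the expected interval by about 10% at 10 per arm and 12% at 20 per arm when r is 0.5, and by about 4% and 6% when r is 0.7. If neither term explains anything, the average cost is 4.0% at 10 per arm and 1.6% at 20. If age group explains 10% of the change, the ratio stays below 1 at every correlation examined for those two sizes. Sample size, SDs, correlation and age effect are all assumptions. The benefit is most plausible for insulin and IGF-1.

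**What to change.** Add to SAP 5.2.2:

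> For insulin and IGF-1 (day 14 of the intervention phase) and for weight and waist (day 14 of the intervention phase and day 14 of the self-maintenance phase), the response is change from baseline. The GLM includes treatment, the baseline value of the same variable and the age group used to stratify randomisation. The adjusted mean difference is reported with its 95% CI; the unadjusted difference is a sensitivity analysis.

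First state the stratum cut-point in section 3.4. Section 5.1.2 gives a cut at 18 only for the subgroup analysis, and section 2.2.3 splits at 18/19 only for case definitions. Leave the planned analysis of mean glucose and gut microbial composition unchanged. Settle the wording before outcome data are seen by arm.

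The cost is two or three sentences, one check of the randomisation record and up to two degrees of freedom. No new data or visits are needed.

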### **3.3. Interventions**

#### **3.3.1. Experimental arm:**

##### **Intermittent caloric restriction**

The experimental intervention is based on the 5:2 diet, which involves caloric restriction for 2 days (consecutive or nonconsecutive, 600 kcal/d for male and 500 kcal/d for female) per week and unrestricted eating during the other 5 days of the week. Total trial duration is one month consisting of a 14-day intervention phase and a 14-day self-maintenance phase. During the maintenance phase, two follow-up electronic questionnaires were conducted.

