## **5. Statistical Analyses**

### **5.1. Primary Outcome Analysis**

#### **5.1.1. ITT analysis of the primary outcome - the primary analysis**

The primary outcome is a binary composite outcome: occurrence of reversal outcome from any cardiometabolic abnormality at the 14th day after dietary intervention phase. The primary analysis will be based on the ITT population as defined above.

The primary endpoint will be summarised by number (%) of subjects that have reverse cardiometabolic abnormality by groups. Statistical analysis will be performed as a two-sided test, using chi-square test for detecting group difference of the percentage. If any subjects dropped off from the

primary endpoint, modified ITT analysis will be performed by using the available subjects.

A generalised linear model (GLM) will be used. In the GLM model, the occurrence of reversal outcome from any cardiometabolic abnormality at the 14th day after intervention phase will be treated as the response variable following a binomial distribution, the treatment as fixed effect and logit link function will be used. From this model, the reversal rate difference and its 95% CIs between two groups will be estimated.

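### The day-28 weight and waist comparisons drop every subject without a day-28 value, although a day-14 value may be on file; one repeated-measures model would use it at little cost

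*SAP*

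**What the plan says.** In this point, day 14 is the end of the intervention phase and day 28 is the 14th day of self-maintenance.

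SAP 2.2.2 lists day-28 outcomes as entries separate from the day-14 changes: "Change in body weight (kg). (Time Frame: from the baseline to the 14th day of the self-maintenance phase" and "Change in waist circumference (cm). (Time Frame: from the baseline to the 14th day of the self-maintenance phase". Weight and waist are the only secondary outcomes listed there at two follow-up times.

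Under 5.2.2 a continuous outcome "will be analysed by a GLM model with treatment as fixed effect and with normal distribution and identity link function". No baseline value, day-14 value, visit term or subject effect is named. On the analysis set, 5.2 says: "Secondary outcome analyses will be based on the ITT population unless specified".

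The only rule for a missing outcome is in 5.1.1, for the primary endpoint: a "modified ITT analysis will be performed by using the available subjects". Section 5.2.1 carries the primary method over to binary secondary outcomes. Nothing carries it over to continuous ones, and no imputation or missing-data sensitivity analysis is described.

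The variable list in section 8 has weight and waist as variables 29 and 30 in the block ending "day after the dietary intervention phase", and as variables 42 and 43 in the block ending "day after the self-maintenance phase". Given the time frames in 2.2.2, I read these as day 14 and day 28.

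The contact described after day 14, in 3.3.1 and likewise 3.3.2, is: "During the maintenance phase, two follow-up electronic questionnaires were conducted".

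**The concern.** A treatment-only GLM uses only subjects who have a response. Someone measured at day 14 but not at day 28 therefore contributes nothing to the day-28 difference. The ITT label describes how subjects are assigned to arms, but the comparison itself is complete-case. Their day-14 value, probably the best available predictor of the missing one, is not used.

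The estimate can then be biased if subjects with a poor day-14 result are lost more often in one arm than in the other. This is possible here: the two diets are plainly different and the SAP describes no blinding. The estimate is also somewhat less precise than it could be. Day-28 weight and waist are the only comparative outcomes measured after the diet ends, so they carry what the trial can say about whether an effect lasts.

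**Working it through.** **No planned figure to reproduce.** The documents give no sample size, SD, effect size or loss rate for these outcomes. The numerical inputs below are assumptions.

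**Assumptions.** 20 per arm; SD of change 1.5 kg; correlation ρ between day-14 and day-28 change 0.6–0.9; no true difference; loss only after day 14.

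**Bias when loss depends on the day-14 result in one arm only.** Let z be the standardised day-14 change, with higher z meaning less weight lost.
- Selective arm: logit P(lost) = logit(p0) + z, a log-odds of 1 per SD.
- Other arm: loss is p0 at random.
- P = E[p(z)] is the loss in the selective arm. The mean z of those retained is m = −E[z·p(z)] / (1 − P).
- Bias of the complete-case difference = 1.5 × ρ × m.
- Approximate standard error = 1.5 × √[1/(20(1 − P)) + 1/(20(1 − p0))].

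Numerical integration over a standard normal z gives E[z·p(z)] = 0.1033, 0.1555 and 0.1855 for p0 = 0.10, 0.20 and 0.30.

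| p0 | P | overall loss (p0 + P)/2 | m | bias, ρ = 0.6 | bias, ρ = 0.9 | SE |
|---|---|---|---|---|---|---|
| 0.10 | 0.134 | 0.117 | −0.1033/0.866 = −0.119 | −0.11 kg | −0.16 kg | 0.50 kg |
| 0.20 | 0.239 | 0.219 | −0.1555/0.761 = −0.204 | −0.18 kg | −0.28 kg | 0.54 kg |
| 0.30 | 0.331 | 0.316 | −0.1855/0.669 = −0.277 | −0.25 kg | −0.37 kg | 0.57 kg |

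For example, 1.5 × 0.9 × (−0.204) = −0.28 kg. The negative sign means that the arm with selective loss looks better than it is. In SD units the bias is ρ × m, so the same multiples apply to waist: 0.07–0.11, 0.12–0.18 and 0.17–0.25 SD.

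Simulations of 4,000 to 6,000 replicates gave the same ranges to within about 0.03 kg. The joint likelihood estimate, which uses the day-14 values of those lost, was within about 0.02 kg of zero throughout.

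**Bias when the same mechanism acts in both arms.** The shift m is then equal in both arms and cancels from the difference. Simulated complete-case bias was no more than about 0.02 kg at up to 33% loss.

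**Precision when loss is random.** With fraction f lost after day 14, the large-sample variance of the joint estimate divided by the complete-case variance is 1 − f·ρ². The complete-case standard error is therefore larger by a factor 1/√(1 − f·ρ²):
- f = 0.10, ρ = 0.6: 1/√0.964 = 1.019, or 2%.
- f = 0.30, ρ = 0.9: 1/√0.757 = 1.149, or 15%.
- ρ = 0.3, f = 0.10 to 0.30: 1/√0.991 to 1/√0.973, or 0.5–1.4%.

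These are large-sample values. At 20–30 per arm, a simulation estimating the day-14 regression separately in each arm found no gain at ρ = 0.5, and sometimes a slight loss.

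**The case against.** The strongest reply is that the bias needs an arm-specific mechanism, and nothing in the documents points to one. That stands: with the same mechanism in both arms the difference is essentially unbiased, and with no loss there is no issue.

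Even in the unfavourable case the bias is modest against the noise. At 22% loss, 0.18–0.28 kg is about a third to a half of a standard error of 0.54 kg. Simulated coverage of the nominal 95% interval was about 0.91–0.94 there, and fell to about 0.89–0.90 only near 31–32% loss with correlation 0.9. This also stands.

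Available-case handling is partly disclosed. Section 5.1.1 states it for the primary endpoint, 6.1 summarises non-missing data, and 5.2.2 reports n by group, so unequal numbers at day 28 would be visible. Visibility does not correct the estimate.

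The correlation is assumed. Section 8 does not say how day-28 weight and waist are obtained. If they are self-reported through the questionnaires, the correlation with day 14 may be lower, and the gain with it.

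A reader might also infer more than the documents support:
- **That these subjects are discarded from the trial.** They leave only the day-28 comparison; their day-14 data still enter the day-14 analyses.
- **That self-maintenance is unsupervised and loss will be high.** The SAP does not describe supervision in either phase, beyond weekly health education during the intervention, and states no expected loss.

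**Conclusion.** The point holds as a low-cost improvement to the analysis of two secondary outcomes of a pilot. As written, the day-28 comparison is complete-case under an ITT label, and relevant collected data go unused.

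Its size cannot be established from the documents. Under the assumptions above, arm-specific loss of 12% to 31–32% gives a bias of about 0.11 to 0.37 kg. For scale, that is 7–25% of the 1.5 kg loss that 2.2.1 counts as reversal of general obesity (0.11/1.5 to 0.37/1.5). Under random loss of 10–30%, the cost is a standard error about 2–15% larger, with almost none at correlation 0.3.

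It would be wrong to conclude that the day-28 result is biased as planned, or that the day-14 primary endpoint is affected. Neither follows.

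**What to change.** In 5.2.2, analyse weight and waist each with one repeated-measures model:
- **Responses:** day-14 and day-28 change from baseline.
- **Fixed effects:** treatment, visit, treatment-by-visit, baseline value and the age stratum used in randomisation (3.4).
- **Covariance and estimation:** unstructured covariance; Stata `mixed` with REML and small-sample degrees of freedom such as Kenward-Roger.
- **Subjects:** every randomised subject with either follow-up value, in the allocated arm.
- **Estimate:** the day-28 difference is the treatment term plus the treatment-by-visit term for day 28, with its 95% CI.
- **Reporting:** number lost between day 14 and day 28, by arm.

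The cost is SAP wording and a little programming in the software already named, with no new data. With complete data and no covariates the model returns the same day-28 difference as the planned GLM. Adding baseline and age stratum makes it an adjusted difference, so the SAP should say so.

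The downside is reliance on missing at random given the day-14 value. This is weaker than what the complete-case comparison needs, but it does not cover loss driven by what happens after day 14. Subjects with no follow-up value at all still contribute nothing, and their number should be stated.

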## **6. General considerations for data analyses**

STATA® (version 15.0) will be used to perform all data analyses and generate the majority of data displays.

